7.1.5. Concomitant medication and treatment

Concomitant medications will be recorded throughout the study, starting from signing on ICF and will include those prescribed for common burn management practice. Any record should include dose, frequency, route, start and stop date and indication.

Unit of blood transfused (whole blood or blood packed cells) with the appropriate volume will be captured for the entire patient's duration in the study and recorded in the concomitant medications form. Any analgesia and anesthesia administered per subject will be recorded in the eCRFs. Incidence & number of procedures for wound care requiring anesthesia will be analyzed.

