7.3.2.2. Secondary target variables

The following secondary endpoints will be evaluated in this study:

Reduction in surgical needs

Reduction of surgical need for excisional eschar removal is measured by an analysis of incidence of surgical eschar removal (tangential/ minor/ avulsion/ Versajet and/or dermabrasion excision).

Earlier eschar removal

The time when complete eschar removal has been achieved will be assessed for each patient on the entire eschar removal period. For definition of complete eschar removal, see Appendix 13.1.1.

Blood loss

Blood loss incurred during the eschar removal procedures will be evaluated. Actual blood loss will be measured by considering the estimated blood loss, changes in Hemoglobin during the eschar removal procedures and the amount of units of blood transfused. Blood loss (Actual Blood Loss, ABL) will be calculated using the following formula [25]:

$$ABL = \frac{EBV * (Hb_{before} - Hb_{after})}{(Hb_{before} + Hb_{after})/2} + V_{WB} + \frac{5}{3} V_{PC}$$

EBV= Estimated blood volume is assumed 70 cm³/Kg

(Hb_{before}- Hb_{after})= Changes in Hb following each eschar removal procedure

V_{WB}= Volume [mL] of whole blood transfused

V_{PC}= Volume [mL] of packed red blood cells transfused.

The ABL will be summed over all procedures carried out to remove eschar, with the Hb measured immediately before each procedure and 4 hours after its completion. The amount of blood transfused will be summed over all transfusions carried out during all debridement procedures and 4 hrs later i.e. the before-after periods that are spanned by these Hb measurements.

Additionally, ABL will also be computed using the formula above, but over the whole eschar removal period (not procedure wise) i.e. the eschar removal process will be considered as one continuous procedure. Therefore, only the Hemoglobin value before the first eschar removal procedure and after the last procedure will be used and all blood transfusions performed between these measurements will be included.

Analyses with both blood loss values will be conducted. However, some missing values are expected. The analysis with less missing values will be regarded as more reliable and is therefore considered the main analysis. The other analysis is considered supportive.

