10.1.1.3. Secondary Endpoint: Blood loss

Missing blood loss values for some eschar removal procedures may occur within a certain patient. A regression model containing main prognostic factors (wound area, depth of wound and type of procedure) for blood loss of eschar removal procedures will be computed on a procedure level treating all procedures as independent. On this basis a multiple imputation will be calculated. The procedure can be described as follows:

1. Test for normality: The Shapiro-Wilk test will be performed on the dataset of non-missing values in each treatment group. The result of these tests will determine the type of the analysis on the imputed data sets (step 3). If the normal distribution hypothesis is not rejected at the 5% significance level in either group, then differences in distribution between NexoBrid and SOC will be tested using a t-test. If the normal distribution hypothesis is rejected either in the NexoBrid group or in the SOC group, then the differences in distribution between the treatment groups will be tested using a Mann-Whitney test.
2. Imputation: Fit a linear regression model with target variable blood loss on a procedure level (as computed in Section 10.3.3.3) and dependent variables size of wounds treated in this procedure (wound area), proportion of area SPT of wounds treated in this procedure (as defined in Section 10.3.3.3.2), proportion of area DPT of wounds treated in this procedure (as defined in Section 10.3.3.3.3), proportion of area FT of wounds treated in this procedure (as defined in Section 10.3.3.3.4) and type of

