procedure (surgical/non-surgical) to the subset containing patients with complete data in those variables for both treatment groups separately. Impute the missing entries of the incomplete data sets $m = 25$ times as follows: Draw a set of regression coefficient from their sampling distribution obtained from fitting the respective linear models outlined above (a different distribution for the regression coefficients will be obtained in the different treatment groups). With these sampled coefficients calculate the predicted blood loss values for the procedures with missing blood loss using the covariate information. To these predicted blood loss values add the realizations of a normally distributed random variable with zero mean and standard deviation equal to the residual standard deviation from the linear model fitted to the complete data set. The random seeds for these 25 imputations will be (11468, 11469, 11470, ..., 11492). On the imputed datasets calculate the blood loss on a patient level.

3. Analysis: Analyze each of the m complete data sets with a t-test or the Mann-Whitney test according to the test result in step 1. This step results in m estimates of the effect and m estimates of the standard deviation.
4. Pooling: Integrate the m analysis results into a final result with the SAS procedure PROC MIANALYZE according to Rubin's combination rules for multiple imputation to obtain the final estimates of mean and variance [28].

For the additional analysis of blood loss which treats the whole eschar removal process as one continuous procedure (see section 7.3.2.2) the multiple imputation will be performed on a patient level. The procedure can be described as follows:

1. Test for normality: The Shapiro-Wilk test will be performed on the dataset of non-missing values in each treatment group. The result of these tests will determine the type of the analysis on the imputed data sets (step 3.). If the normal distribution hypothesis is not rejected at the 5% significance level in either group, then differences in distribution between NexoBrid and SOC will be tested using a t-test. If the normal distribution hypothesis is rejected either in the NexoBrid group or in the SOC group, then the differences in distribution between the treatment groups will be tested using a Mann-Whitney test.

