2. Imputation: Fit a linear regression model with target variable blood loss on a patient level (as computed in Section 10.3.3.3) and dependent variables wound area, depth of wound (categorized as described in Section 11.1.10) and course of debridement procedure (as defined in Section 10.3.3.3.5) to the subset containing patients with complete data in those variables for both treatment groups separately. Impute the missing entries of the incomplete data sets $m = 25$ times as follows: Draw a set of

regression coefficient from their sampling distribution obtained from fitting the respective linear models outlined above (a different distribution for the regression coefficients will be obtained in the different treatment groups). With these sampled coefficients calculate the predicted blood loss values for the procedures with missing blood loss using the covariate information. To this predicted blood loss values add the realization of a normally distributed random variable with zero mean and standard deviation equal to the residual standard deviation from the linear model fitted to the complete data set. The random seeds for these 25 imputations will be (12467, 12468, 12469, ..., 12491). On the imputed datasets calculate the blood loss on a patient level.

3. Analysis: Analyze each of the m complete data sets with a t-test or the Mann-Whitney test according to the test result in step 1. This step results in m estimates of the effect and m estimates of the standard deviation.
4. Pooling: Integrate the m analysis results into a final result with the SAS procedure PROC MIANALYZE according to Rubin's combination rules for multiple imputation to obtain the final estimates of mean and variance [28].

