10.3.3.3. Secondary Endpoint: Blood loss

10.3.3.3.1. Blood loss for main analysis

For each patient and each procedure carried out to remove eschar the estimated blood volume (EBV) will be calculated as

$$EBV = 70 \frac{cm^3}{kg} * weight(kg)$$

Furthermore, the total volume of whole blood and packed red blood cells (PRBC) transfused (in milliliters) will be calculated per procedure (transfusions given during the procedure and 4 hours \pm 15 minutes later) and denoted by V_{WB} and V_{PC} in the following.

From these quantities, the blood loss (Actual Blood Loss, ABL) will be calculated using the following formula [25]:

$$ABL = \frac{EBV * (Hb_{before} - Hb_{after})}{(Hb_{before} + Hb_{after})/2} + V_{WB} + \frac{5}{3}V_{PC}$$

The factor of 5/3 is derived from chapter 5 of Transfusion Medicine, 4th Edition [31] and compensates for the fact that equal volumes of whole blood and packed red blood cells are not comparable.

The ABL will be summed over all procedures carried out to remove eschar, with the Hb measured immediately before each procedure and 4 hours after its completion. The amount of blood transfused will be summed over all transfusions carried out during the debridement procedure and 4 hrs later i.e. the before-after periods that are spanned by these Hb measurements.

Additionally, blood loss will be computed considering the whole debridement process as one continuous procedure. For this value, the formula for ABL given above will also be used. However, the ABL will be computed using the Hb measured immediately before the first procedure and 4 hours after completion of the last procedures. The amount of whole blood and packed red blood cells (PRBC) transfused will be calculated as before, but incorporating all such transfusions in the time frame spanned by the Hb measurements used for the calculation (pre first procedure to 4 hrs post last procedure (in which complete debridement was achieved).

Analyses with both blood loss values will be conducted. However, some missing values are expected. The analysis with less missing values will be regarded as more reliable and is therefore considered the main analysis. The other analysis is considered supportive.

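### When only a hemoglobin is missing, the blood-loss imputation redraws the whole ABL and leaves the recorded transfusion, body weight and available hemoglobin unused

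*SAP*

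**What the plan says.** Section 10.3.3.3.1 of the SAP defines ABL for each eschar removal procedure as

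ABL = EBV × (Hb_before − Hb_after) / mean of the two Hb values + V_WB + 5/3 × V_PC.

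The blood volume comes from body weight (section 7.3.2.2: "EBV= Estimated blood volume is assumed 70 cm³/Kg"). Packed cells carry a weight of 5/3 ("The factor of 5/3 is derived from chapter 5 of Transfusion Medicine, 4th Edition [31] and compensates for the fact that equal volumes"). The transfusion window is fixed by clock time: "The amount of blood transfused will be summed over all transfusions carried out during the debridement procedure and 4 hrs later". Transfusions are recorded whether or not a hemoglobin was drawn (section 7.1.5: "Unit of blood transfused (whole blood or blood packed cells) with the appropriate volume will be captured for the entire patient's duration in the study"). Weight is a baseline item (section 7.3.1).

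For missing values, section 10.1.1.3 announces "A regression model containing main prognostic factors (wound area, depth of wound and type of procedure) for blood loss of eschar removal procedures". The imputation step reads "Fit a linear regression model with target variable blood loss on a procedure level (as computed in Section 10.3.3.3"), with treated wound area, the SPT, DPT and FT proportions and surgical or non-surgical type as covariates, fitted separately by arm. Missing entries are then filled: "With these sampled coefficients calculate the predicted blood loss values for the procedures with missing blood loss using the covariate information", plus a normal residual. The version that treats eschar removal as one continuous process is imputed per patient from "dependent variables wound area, depth of wound (categorized as described in Section 11.1.10) and course of debridement procedure".

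Blood loss is fourth in the testing hierarchy (section 11.1.8). The ABL version with fewer missing values becomes the main analysis (section 10.3.3.3.1), so either imputation model may feed that test.

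**The concern.** ABL cannot be computed when one hemoglobin is missing, yet the rest of the formula is normally still known: the transfused volume, the weight and often the other hemoglobin. Neither imputation model uses any of these, and no rule in the SAP retains the known part. A patient with two packed units on record and one missed sample is imputed as if nothing were known about transfusion.

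Transfusion marks heavy bleeding. Leaving it out shrinks transfused procedures toward the mean of procedures with similar wounds and inflates the untransfused ones. It also makes the result depend on a stronger assumption than necessary, namely that missed hemoglobins are unrelated to transfusion given wound area, depth and type or course of procedure. What is at stake is the precision and robustness of a hierarchically tested secondary endpoint.

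**Working it through.** The SAP gives no sample size, SD, transfusion rate or missing-data rate for blood loss, so there is no figure of its own to reproduce. Clinical inputs below are assumptions unless a section is named.

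**1. What the known part is worth.** With two packed units of 250, 300 or 350 mL, the transfusion term is 5/3 × 500 = 833, 5/3 × 600 = 1000 or 5/3 × 700 = 1167 mL.

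- At 80 kg, EBV = 70 × 80 = 5600 mL. With Hb 12 → 11 and two 300 mL units, ABL = 5600 × 1/11.5 + 1000 = 487 + 1000 = 1487 mL.
- With Hb 12.0 → 12.5 and one 300 mL unit, ABL = 5600 × (−0.5)/12.25 + 500 = −229 + 500 = 271 mL. A transfused procedure need not have a large ABL.
- An imputed ABL of 0 beside a recorded 1000 mL would need 5600 × (12 − x)/((12 + x)/2) = −1000. This gives x ≈ 14.4: a rise of about 2.4 g/dL from 12. Nothing in the model makes such a draw unlikely.

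**2. One-arm simulation.** 200,000 procedures per scenario: weight about 80 kg (SD 15); wound area 3–15% TBSA; Hb before about 12.5 (SD 1.5); Hb drop averaging 0.8 + 0.05 × area (SD 0.7) if untransfused and 0.5 (SD 1.0) if transfused; 1 + Poisson(1) units of 300 mL. The plan's method is simplified to whole ABL on wound area. The alternative imputes the Hb term from area, weight, Hb before and transfused yes/no, then adds the recorded volume. Figures in mL:

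| Transfused share | Hb missing, transfused / untransfused | True mean, transfused with Hb missing | Plan | Hb term only | Arm mean: true → plan |
|---|---|---|---|---|---|
| 5% | 20% / 20% | 1254 | 681 | 1258 | 642 → 642 |
| 5% | 40% / 15% | 1250 | 662 | 1250 | 643 → 634 |
| 20% | 20% / 20% | 1254 | 784 | 1267 | 733 → 734 |
| 20% | 40% / 15% | 1244 | 748 | 1247 | 733 → 703 |
| 40% | 20% / 20% | 1259 | 912 | 1258 | 855 → 854 |
| 40% | 40% / 15% | 1251 | 872 | 1255 | 854 → 811 |
| about 75% | 20% / 20% | 1252 | 1128 | 1256 | 1067 → 1067 |
| about 75% | 40% / 15% | 1254 | 1109 | 1254 | 1073 → 1041 |

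- The shortfall runs from (1252 − 1128)/1252 = 10% to (1250 − 662)/1250 = 47%.
- With equal missingness the arm mean is right because the errors cancel: at 20% transfused, untransfused procedures are imputed at 725 mL against a true 604.
- With unequal missingness the arm mean is 9 to 43 mL too low.
- The imputation residual SD at 20% transfused and equal missingness falls from 530 to 396 mL with the alternative.
- Across all scenarios run, 43–68% of imputed values for transfused procedures lay below their own transfusion term. That is not impossible in itself, since it only implies an Hb rise. Under the assumed drop (mean 0.5, SD 1.0) the true share is Φ(−0.5) = 31%.

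**3. Two-arm simulation.** 75 + 75 patients (section 9.3.1), 24% and 60% excised (section 9.2), and an assumed 14% or so of surgical procedures transfused; 400 replicates, 5 imputations each. SOC minus NexoBrid mean difference, full data / plan / Hb imputation:

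- Hb missing in 10% of untransfused and 30% of transfused procedures: 298 / 288 / 298 mL, so the plan is 10/298 = 3% low.
- 15% and 45%: 302 / 281 / 299 mL, so 21/302 = 7% low.
- 20% and 20%: 307 / 308 / 307 mL, no bias.

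**The case against.** Three stronger readings are tempting, and the SAP does not support them.

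- *All remaining hemoglobins are discarded.* In the procedure-level version only procedures with a missing ABL are replaced; the patient's other procedures keep their observed ABL and are summed. In the whole-process version intermediate hemoglobins are outside the formula even with complete data (section 7.3.2.2). They are merely not used as auxiliary predictors.
- *Every transfused patient is imputed far too low.* The shortfall is an average, and its size depends on transfusion rates and unit volumes that the SAP does not state. A procedure with a net Hb rise, such as the 271 mL example, can be imputed too high.
- *The treatment comparison is biased.* That needs hemoglobin to be missed more often in transfused procedures, which nothing in the SAP shows. The one scheduled gap concerns non-surgical procedures (Table 1 footnote: pre-procedure assessments for surgical procedures only; post-procedure assessments after a non-surgical procedure only if it is the last). Procedure type or course is already in the models. If transfusion is concentrated in SOC, the bias would understate SOC loss and so would not favour NexoBrid.

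The test may also be little affected. If normality is rejected in either arm, a Mann-Whitney test is used, which depends less on extreme values. In a further simulation with assumed inputs (75 + 75, 600 replicates, 5 imputations, median p), its power under the plan versus Hb imputation was 50% vs 51%, 47% vs 51% and 50% vs 47% in the three missingness patterns above. With a Monte Carlo standard error near √(0.25/600) = 2 points for each figure, these show no consistent change.

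Transfused volume and Hb change are also reported separately (sections 11.1.4.11 and 11.1.5.7). That informs the reader but does not repair the imputed ABL.

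A practical objection stands. The models are fitted by arm, and 75 × 0.24 × 0.14 ≈ 2.5 transfused NexoBrid patients (assuming about one surgical procedure each) cannot support an arm-specific transfusion coefficient. The fix must allow for this.

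These points limit the consequence. They leave the omission itself in place.

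**Conclusion.** The point holds in a limited form. When only a hemoglobin is missing, both imputation models replace the whole ABL and ignore components of it that are on record. Transfused procedures are then pulled toward untransfused ones (about 10% to 47% low on average in the scenarios run), and individual imputed values can sit badly with the recorded transfusion.

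Arm means are biased only if missing hemoglobin is related to transfusion. Under the assumed imbalances this was 9 to 43 mL in an arm mean, or 3% to 7% of the arm difference, probably against NexoBrid. Otherwise the cost is lost precision and implausible single values. All sizes rest on assumed transfusion rates, unit volumes, Hb changes and missing-data rates. This is a cheap improvement of minor to moderate severity; it does not threaten the trial's conclusions.

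**What to change.** Amend the imputation step of section 10.1.1.3 in both versions:

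1. Impute only the missing hemoglobin, or only the hemoglobin term of ABL.
2. Keep the existing covariates and add weight (or EBV), the available Hb and the transfused volume V_WB + 5/3 × V_PC. In the whole-process version the available Hb includes the last one measured.
3. Compute ABL by the formula in section 10.3.3.3.1, with the recorded transfused volume kept as observed.
4. Where an arm has too few transfused procedures to estimate a transfusion coefficient, use a coefficient common to both arms in a model with an arm term. State in the SAP how few is too few.

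The cost is a change of SAP wording, slightly more programming and a somewhat larger imputation model. Every variable is already collected. The downside is the assumption of a common transfusion coefficient where transfusions are sparse, which should be stated.

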10.1.2. Safety Endpoints

10.1.2.1. Safety Endpoint: Time to reach complete wound closure

The analysis of the safety endpoint time to complete wound closure will compute missing values as censored at the date of the last non-missing wound closure assessment.

10.1.2.2. Safety Endpoint: Cosmesis and function at 12 months from wound closure

A higher ratio of missing values is expected in the case of later MVSS values, especially for 24 months. It is expected that the 1 months MVSS value exists. If this is not the case the missing MVSS value will be replaced by the mean MVSS value of all patients who belong to the same treatment group and the same stratum (see Section 11.1.10) at that time point. For missing MVSS values at later time points (3, 6, 12, 18 and 24 months) the following imputation method will be used:

For each time point (1, 3, 6 and 12 months) and each treatment arm separately, a linear regression model with target variable MVSS at 12 months and explanatory variables MVSS at the respective time point and all stratification variables (see Section 11.1.10) is fitted to the data of patients having both MVSS values. Missing MVSS values at 12 months are then

imputed with the prediction of the linear regression model, which has the last non-missing MVSS value before the 12 months measurement for the individual as explanatory variable (i.e. for patients who have the 6 months MVSS measurement but not the 12 months measurement, the 12 months measurement is imputed from the 6 months measurements; for those who have the 3 months measurement but not the 6 months or 12 months measurement the 12 months measurement is imputed from the 3 months measurement; and for those who have the MVSS measurement at 1 month but not at 3 months, 6 months or 12 months the 12 months measurement will be imputed from the 1 month measurement). To this prediction, the realization of a normally distributed random variable with zero mean and standard deviation equal to the residual standard deviation from the linear model is added. The random seed for this imputation is 45318.

Similarly, for each time point (1, 3, 6, 12 and 18 months) and each treatment arm separately, a linear regression model with target variable MVSS at 24 months and explanatory variables MVSS at the respective time point and all stratification variables (see Section 11.1.10) is fitted to the data of patients having both MVSS values. Missing MVSS values at 24 months are then imputed with the prediction of the linear regression model, which has the last non-missing MVSS value before the 24 months measurement for the individual as explanatory variable. To this prediction, the realization of a normally distributed random variable with zero mean and standard deviation equal to the residual standard deviation from the linear model is added. The random seed for this imputation is 45448.

Using this imputation method deviates from the handling of missing data specified in the protocol. There, simple LOCF was intended. However, LOCF is not considered a suitable imputation method for the MVSS values as early MVSS values are not considered representative for late MVSS measurements in the same individual. Furthermore, LOCF is heavily criticized in the statistics community since it may lead to biased results even when the missing occurs completely at random (see [29], [30]).

Additionally, best case – worst case imputations will be used as a supporting sensitivity analysis. One using the worst case MVSS value of 9 (observed maximum MVSS value in the SOC group in the previous study MW2004-11-02) for all missing MVSS data and one using the best case value of 0 (observed minimum MVSS value in the SOC group in the previous study MW2004-11-02).

10.1.2.3. *Safety Endpoint: Cosmesis and function at 24 months from wound closure*

See 10.1.2.2.

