7.1. General Information of Trial Design

This is a multi-center, multi-national, randomized, controlled, assessor blinded, three-arm study aiming to demonstrate superiority of NexoBrid treatment over Gel vehicle control and over SOC treatment in thermal burn subjects with burns.

One hundred and seventy five subjects (175 subjects) are planned to be randomized to the study in a 3:3:1 ratio (NexoBrid: SOC: Gel Vehicle). The study will be conducted at sites in the US and out of the US.

Following the enrollment of a patient to the study and prior to randomization, physicians will identify one or more TWs per patient according to the TW definitions described in Section 1.1 of the protocol.

All subjects' DPT and FT burns that comply with the specified entrance criteria under Section 7.1.3 are intended to receive study treatment per the randomized study arm and therefore, must be designated as TWs. This will further allow an evaluation of the subject systemic safety by allowing treatment of the subject's entire deep burns as per the randomized study arm. After reviewing the entrance criteria, prior to randomization, eligible subjects will be stratified into different groups in order to standardize and minimize bias between study groups in terms of efficacy and safety outcomes that are expected to be correlated to the patient total burn area and its depth. Please refer to Section 13.7.1 of the protocol for full description of the randomization procedure.

Following the stratification, patients will be randomized as per their stratification group (see Section 11.1.10) in a 3:3:1 ratio (NexoBrid: SOC: Gel Vehicle).

Patients will be treated in the same way in all study arms (NexoBrid, SOC or Gel vehicle) except for the eschar removal stage which will be performed as per the randomization study arm.

Prior to initiation of eschar removal treatment subjects will be medicated with appropriate analgesia (please refer to Appendix 2- Pain Management Procedures of the protocol) and undergo wound cleansing and dressing of all wounds with antibacterial solutions (as specified

in Section 8.1 of the protocol). Following wound cleansing and antibacterial treatments, subjects will undergo the eschar removal process as per treatment assignment (NexoBrid, SOC or Gel Vehicle, following randomization) as further described in *APPENDIX 16- Treatment Diagram of the protocol*.

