7.2. Trial schedule

The healing and care of the burn wound may be divided into the three distinctive phases:

1. Eschar removal treatment phase (until complete eschar removal)
2. Wound management (until complete wound closure)
3. Scar modulation and maturation

These phases are common to the care of all wounds and are well defined in acute wounds such as burns.

In this study, these phases and their treatment strategy are equal for all arms, NexoBrid, SOC, and Gel Vehicle, following the ABA white paper recommendations [24].

The total duration of the study treatment and follow up period of each participating subject is expected to be 25 months: following the Eschar removal procedure, each subject will be followed up weekly (Weeks 1, 2, 3 and 4 etc.) until complete wound closure is achieved and 2 weeks later for wound closure confirmation, for each of the subject's TWs. Long-term follow-up visits will be performed at 1, 3, 6, 12, 18 and 24 months post last wound closure confirmation visit (for details see Table 1).

Table 1: Treatment flow chart - all arms³

If applicable
 * Weekly FU assessments will be performed every 7± 2 days from start of treatment until complete wound closure. Long-term FU will be performed 1,3,6,12,18 and 24 M after last wound closure confirmation.
 **First treatment session will include any procedure for eschar removal: the NexoBrid®/Gel Vehicle/Surgical or non-surgical procedure, as per randomization arm
 ** Procedure can be either surgical or non-surgical. A whole period of continuous dressing changes (from first coverage application to last coverage application) is considered as one non-surgical procedure, assessments should not be repeated for each dressing change; Pre procedures assessments refer only to surgical procedures. Post procedures assessments refer to any surgical procedures and for non-surgical procedure only if it is the last procedure

Parameter	Screening tests	Baseline within 1 h Pre First treatment session - All arms	Topical arms (NexoBrid or Gel Vehicle): (refer to first and second application). S=Soaking, R=Removal	SOC procedures** (including additional procedures in the topical arms)	Daily assessments	Management & Re-admissions ⁴ - surgical procedures assessment	Wound	HD or premature discontinuation visit	Weekly FU*	Long-Term FU (1, 3, 6,12,18 & 24 months)*
Inform Consent signing	X									
Medical history	X									
Burn History ⁵	X									
ConMeds & AEs	X	X	X	X	X	X	X	X	X	X

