9.3.1. Summary of sample size

Although the maximum sample size from the above calculations is a total of 121 patients (65 in the NexoBrid group, 13 in the Gel vehicle group and 43 in the SOC group (to match NexoBrid numbers)), we propose entering larger numbers to provide an extra margin of assurance in achieving positive results on the efficacy outcomes, and adequate information on safety outcomes to allow better benefit vs. risk assessment.

Therefore, we plan a study with total sample size of 175 patients; 75 (NexoBrid) + 75 (SOC) + 25 (Gel Vehicle).

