11.1.10. Stratification

The following factors are used to stratify the study design:

A. Total TBSA % per patient

A1: Total TBSA <=15%

A2: Total TBSA >15%

B. Overall depth per patient

B1: All TWs are full thickness;

B2: Mixed TWs – full thickness and deep partial thickness

B3: All TWs are deep partial thickness.

C. Center Group, to address possible differences in SOC procedures between sites (if any), to allow comparison of the results within group of centers and to reduce the likelihood of a group of centers including patients in only one arm of the study (5 groups of centers were formed based on similarity of SOC practice).

These factors are accounted for in the analyses of the primary and secondary endpoints by including them as adjusting variables.

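### The 1-month MVSS fill-in by arm-and-stratum mean can be undefined or rest on one patient, and patients whose closure is never confirmed have no MVSS rule of their own

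*SAP*

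**What the plan says.** Section 10.1.2.2 opens from an expectation: "It is expected that the 1 months MVSS value exists". Where it does not, the rule is this: "the missing MVSS value will be replaced by the mean MVSS value of all patients who belong to the same treatment group". The donors must also share the patient's stratum and be measured at that visit. Missing 12- and 24-month values are then predicted by a linear regression, fitted separately in each arm, on the last earlier MVSS and all stratification variables. One random residual is added to each prediction.

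The strata come from section 11.1.10: two TBSA levels, three depth levels, and center group, where "5 groups of centers were formed based on similarity of SOC practice". Section 9.3.1 plans "75 (NexoBrid) + 75 (SOC) + 25 (Gel Vehicle").

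The MVSS clock starts at closure: "Long-term follow-up visits will be performed at 1, 3, 6, 12, 18 and 24 months post last wound closure confirmation visit" (section 7.2; likewise 7.1 and 7.3.3.2). Section 10.3.4.1 foresees wounds that never close and censors them for time to closure. No MVSS rule refers to them.

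The tested quantity is the adjusted NexoBrid minus SOC difference in MVSS. Non-inferiority is concluded if the upper 95% limit is below 1.9 (sections 11.2.4.2 and 11.3.4.3). Section 10.1.2.2 also plans two sensitivity runs, one with 9 and one with 0 for every missing MVSS. Sections 11.2.8 and 11.3.8 label the testing at these stages exploratory.

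**The concern.** A mean within arm and stratum needs at least one other patient in that cell with an observed 1-month value. With 30 cells per arm this cannot be relied on, and the SAP does not say what happens in an empty cell. The gap would have to be filled by an unplanned choice after the data are in, in a section that otherwise fixes even the random seeds. With one donor, the mean is simply that person's score.

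The second issue is who lacks all MVSS values. Some will have dropped out. Others, by the visit clock, will have a wound whose closure was never confirmed. Because the clock runs from the last confirmation, one open wound can remove the whole patient. The general rule then predicts that patient's score from patients in the same arm who healed. If non-closure were commoner on NexoBrid, the main MVSS comparison would lean towards non-inferiority, while objective 3 (section 2.2) is to show no unacceptable harm on wound closure and on long-term cosmesis and function.

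**Working it through.** **Inputs from the SAP.** 175 patients at 3:3:1 (section 7.1): 175 x 3/7 = 75, 75, and 175 x 1/7 = 25, which reproduces section 9.3.1. Strata: 2 x 3 x 5 = 30 (section 11.1.10). Margin 1.9. MVSS range 0 to 18 (section 10.3.4.2). The SAP gives no stratum sizes, no expected number without MVSS and no number of non-closers.

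**Cell size.** 75/30 = 2.5 per cell in NexoBrid and in SOC. This average includes the patient with the missing value; the expected number of possible donors is 74/30 = 2.47.

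**Chance of too few donors.** For a patient in a cell of probability p with m other patients in the arm, P(no donor) = (1 - p)^m and P(one donor) = m p (1 - p)^(m-1), averaged over cells with weight p. With equal cells and m = 74:

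- no donor: (29/30)^74 = 8.1%
- exactly one: 74 x (1/30) x (29/30)^73 = 20.8%

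The following variations use assumed stratum margins. The mild skew is TBSA 80/20, depth 20/40/40, centers 30/25/20/15/10. The strong skew is 90/10, 10/30/60, 40/25/15/12/8.

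| Margins | Other patients also missing | No donor | One donor | Expected empty cells of 30 (75 patients) |
|---|---|---|---|---|
| Equal | 0% | 8.1% | 20.8% | 2.4 |
| Equal | 10% | 10.5% | 24.0% | 2.4 |
| Mild skew | 0% | 9.1% | 12.9% | 6.9 |
| Mild skew | 10% | 10.5% | 14.4% | 6.9 |
| Strong skew | 0% | 7.9% | 8.6% | 11.9 |
| Strong skew | 10% | 8.8% | 9.4% | 11.9 |

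The no-donor chance is stable at 8% to 11%. The one-donor share depends on the margins.

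**How many patients.** These percentages apply only to patients who need the rule. With an assumed 2 to 8 per arm, the expected number without a donor is between 2 x 0.08 = 0.2 and 8 x 0.11 = 0.9.

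**What the two steps produce.** The rule was simulated with an assumed 12-month arm mean of 4, SD 2.5, correlation 0.5 between months 1 and 12, mild skew, and 2, 4 or 8 patients without any MVSS. Where a donor existed, the imputed 12-month values averaged 3.99 to 4.04 with SD about 2.4. The patients are therefore average in expectation, but are not each given the mean, and small cells cause no material bias. The no-donor share was 8.3% to 10.5%.

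**Size of the non-closure effect.** If k of 75 NexoBrid patients and no SOC patient never close, and their true score would lie d points above average, the main analysis understates the difference by k x d/75:

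- k = 1, d = 5: 5/75 = 0.07, or 4% of 1.9
- k = 4, d = 5: 20/75 = 0.27, or 14% of 1.9

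Both k and d are assumptions; d = 5 takes an assumed mean of 4 and the plan's worst-case value of 9.

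**The case against.** The strongest reply is that the plan already scores all missing MVSS as 9. With four non-closers on NexoBrid, none on SOC, mean 4, and 10 drop-outs in each arm, that run gives (61 x 4 + 14 x 9)/75 = 4.93 against (65 x 4 + 10 x 9)/75 = 4.67, a difference of 0.27. The shift is then visible. What remains is that the run treats every cause of missingness alike in both arms. With four NexoBrid non-closers and four SOC drop-outs only, both arms move by 4 x 5/75 = 0.27 and the shift disappears; it is masked whenever SOC drop-out is sufficiently higher. The value 9 is also only half the scale range.

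Non-closure has its own non-inferiority analysis, on the FAS with a 7-day margin (section 11.1.4.1), so it does not go unexamined. The timing of the first-stage analysis in section 11 also suggests that closure is expected. Both points stand and limit the consequence.

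A reader might infer three stronger things that the SAP does not support.

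- That about 8% of all patients get no value: the percentage applies only to those who need the rule. A patient who missed month 1 but was seen later, before the tested visit, is predicted from that later value.
- That never-closed patients receive the mean as their tested score: the cell mean fills month 1 only, and a regression with a random residual supplies months 12 and 24.
- That the MVSS result would conceal a large harm: a shift of (4/75) x (18 - 4) = 0.75 units needs all four patients at the scale maximum, while the worst SOC value that the SAP cites from the earlier study is 9.

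**Conclusion.** The concern holds as a gap in a rule that is likely to reach few patients. For a patient with no MVSS before the tested visit, the starting value can be undefined (about 8% with equal cells, 8% to 11% under the assumed variations) or rest on a single donor (about 21% with equal cells, 9% to 24% across the variations). This takes the mean-filled month-1 value as the input to the later regression, which the SAP implies but does not state outright.

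The non-closure point is secondary. That such patients have no MVSS is an inference from the visit clock; the SAP does not say so. The size is illustrative, 0.07 to 0.27 units in the cases shown, and would be near zero if non-closers are few or balanced between arms. The tests concerned carry formal hypotheses and a rejection rule, and section 6.4 has them programmed twice, but they are labelled exploratory, and section 11 calls the first-stage analysis the only inductive one. This calls for a correction to the SAP wording; it does not threaten the trial's main conclusions.

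**What to change.** In section 10.1.2.2, drop the cell mean. For a patient with no earlier MVSS, predict the 12- and 24-month values from an arm-specific linear regression on the stratification main effects, plus a random residual with a stated seed. This is the regression that the SAP already uses, without the earlier MVSS term. It needs 1 + 1 + 2 + 4 = 8 coefficients per arm in place of 30 cell means, and is defined whenever each factor level has observed patients in the arm.

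Report by arm how many patients have no MVSS because closure was never confirmed, separately from drop-out. Add one supportive run of the comparison with 1.9 in which only the never-closed patients get a poor score, at least the worst observed value, and all other missing values follow the main rule. Keep the 0 and 9 runs.

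The cost is a few sentences in the SAP and one extra run. The MVSS result may become slightly less favourable.
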